Title: Intelligent Personal Assistant for Managing Depression in Homebound Older Adults

NCT Number: NCT04900272

Document Date: October 22, 2021

STU#: STU00212384

PROTOCOL TITLE: Intelligent Personal Assistant for Managing Depression in Homebound Older Adults

PRINCIPAL INVESTIGATOR:

[name]
 General Internal Medicine and Geriatrics
 [contact]
 [contact]

VERSION DATE: October 22, 2021

STUDY SUMMARY:

Investigational Agent(s) (Drugs or Devices)	N/A
IND / IDE / HDE #	N/A
Indicate Special Population(s)	 Children  Children who are wards of the state  Adults Unable to Consent  Cognitively Impaired Adults  Neonates of Uncertain Viability  Pregnant Women  Prisoners (or other detained/paroled individuals)  Students/Employees
Sample Size	50 stakeholders & 40 older adults
Funding Source	Northwestern Older Americans Independence Center Pilot/Exploratory Studies Core
Indicate the type of consent to be obtained	 Written  Verbal/Waiver of Documentation of Informed Consent  Waiver of HIPAA Authorization  Waiver/Alteration of Consent Process
Site	 Lead Site (For A Multiple Site Research Study)  Data Coordinating Center (DCC)
Research Related Radiation Exposure	 Yes  No
DSMB / DMC / IDMC	 Yes  No

STU#: STU00212384

OBJECTIVES:

The objective of this pilot study is to design a companion booklet and pilot test it with a voice-controlled intelligent personal assistant (VIPA), Google Home or Amazon Alexa, to provide patients with skills and tools to help manage their social isolation. The companion booklet is a document that will be created using feedback obtained from a panel of geriatric experts, highlighting features of the VIPA that may be most beneficial to socially-isolated older adults. It will be submitted to the IRB for approval once finalized. The specific aims of this project are to:

Aim 1: Design a companion booklet to be used in conjunction with a VIPA (Google Home/Amazon Alexa) for improving social isolation and communication among homebound older adults, defined as someone who is unable to leave the home without assistance of a device or another person, due to a physical or cognitive condition.

Aim 2: Assess the feasibility and implementation of the VIPA (Google Home/Amazon Alexa) and the companion booklet and its impact on clinical and functional outcomes for older adults with social isolation.

BACKGROUND:

Loneliness and social isolation are both common in older adults in the US. In a prospective survey of a US population based cohort, 17.6% of adults over 65 years of age endorsed feeling lonely "much of the time" (Donovan et al.). And, according to Landerio and colleagues, up to 50% of those aged over 60 are at risk of social isolation.

Social distancing, which may necessitate increased isolation, is an essential public health strategy during a pandemic such as COVID-19, especially for those at increased risk of morbidity and mortality (Centers for Disease Control). Older adults are one such group facing an increased risk from COVID-19; in the United States, between 31-70% of adults aged 65 and older with confirmed COVID-19 infection have required hospitalization and 8/10 reported deaths due to COVID-19 have been in adults older than 65 years of age (Centers for Disease Control). According to Armitage and Nellums however, self-isolation will have a disproportionate impact on elderly individuals, who may not have close friends and family, and whose social contact can be dependent on activities taking place outside the home (ex: at places of worship).

In a population-based Swiss cohort, independent of age, socially isolated individuals had increased risk of poor health, including poor self-rated health and presence of musculoskeletal disorders, moderate-severe depression, and multiple other comorbidities (Hammig). The same cohort also demonstrated an increased risk of unhealthy behaviors, such as physical inactivity, poor diet, and psychotropic drug use in socially isolated individuals (Hammig). In a population-based cohort in the US, loneliness was associated with a 20% increased rate of cognitive decline in adults over 65 years, independent of socio-demographic factors, social network, poor health, and baseline depression (Donovan et al.).

The impact of COVID-19 necessitated social distancing and consequent loneliness on the health of older adults is an acute public health concern. First, COVID-19 related changes in the health system may impair the physical and mental health of older adults--especially those who are frail, very old, or with multiple comorbidities--due to changes in diet, exercise, social stimulation, and accessibility of functional supports (Steinman et. al.). Furthermore, based on lessons learned from previous pandemics such as SARS and MERS, social distancing and the loneliness and/or social isolation that could accompany it may have a negative impact on mental health (Venkatesh and Edirappuli). Factors such as maintaining a healthy lifestyle and hobbies, virtual social interactions,

STU#: STU00212384

and mindfulness may help to mitigate these effects (Venkatesh and Edirappuli). Thus, strategies ought to be implemented to mitigate the risk of increased morbidity and of infection from COVID-19 due to the effects of isolation on the mental and physical health of the elderly (Armitage and Nellums) (Landerio et al).

Chen and Schulz found that information and communication technology strategies show promise in reducing social isolation in the elderly, but recognize that more information is needed regarding the efficacy of different interventions for different individuals (Chen and Schulz). Online technologies can be used to help provide a stronger sense of belonging and support for elderly individuals (Armitage and Nellums).

Older adults have often been on the fringe of benefitting from technology. However, VIPAs (e.g. Google Home, Amazon Echo) may be useful to homebound older adults with social isolation, connecting them to caregivers and primary care; providing functional, cognitive, and social stimulation.

STUDY ENDPOINTS:

For Aim 1, the study endpoint will be the finalized VIPA companion booklet for use in the pilot.

For Aim 2, the study endpoint will be the completion of the 16 week pilot program.

STUDY INTERVENTION(S) / INVESTIGATIONAL AGENT(S):

The VIPA accompanying instructional booklet focused on social-isolation in older adults that will be designed for this project will assist older adults with socialization, goal setting, monitoring, feedback and reminders.

PROCEDURES INVOLVED:

In Aim 1, a panel of geriatric experts and patients (n=15-50) will be recruited to help identify which applications available on the VIPA (Google Home/Amazon Alexa) may be the most useful for homebound older adults who may be socially isolated. Stakeholders will include geriatricians (attending physicians), nurses, social workers, patients, and caregivers of older adults. Stakeholders (geriatric experts) will independently use the Google Home or Amazon Alexa Assistant as a trial themselves for 2-4 weeks, and then select those VIPA features that they think may be the most relevant and useful for older adults to help minimize social isolation.

Or, in the case of older adults and caregivers, they will be given the device, and either the study PI or Research Study Coordinator (RSC) will visit the participant's home, or assist the patient virtually, to set up the Google Home or Amazon Alexa device. Participants will then provide feedback about the device after 2-4 weeks of use. This feedback will be collected over the phone with the Research Study Coordinator or online. Once responses are collected, the feedback will be implemented into an updated iteration of the companion booklet, which will be used for Aim 2.

Based on the collective feedback from the geriatric expert and patient panel, we will design a finalized companion booklet to go along with the VIPA, highlighting the list of applications that may benefit older adults with social isolation. Once the VIPA companion booklet is updated, the stakeholders will review the booklet and provide feedback via a second online survey (or via telephone if unable to complete online) before it is finalized and is ready to be used in Aim 2 in the pilot study. The goal is a VIPA companion booklet along with the VIPA that will assist older adults with socialization, goal setting, monitoring, feedback and reminders.

STU#: STU00212384

For Aim 2, we will recruit a total of 20-40 older adult homebound patients who are likely to be socially isolated to use the VIPA and accompanying instructional booklet focused on social-isolation. Either the study PI or Research Study Coordinator (RSC) will visit the participant's home, or assist the patient virtually, once consented, to set up the Google Home or Amazon Alexa device for them and review the companion VIPA booklet with them. For Aim 2, participants will be asked to use the VIPA and accompanying second iteration of the instructional booklet focused on social-isolation. These participants will be surveyed over the phone, online, or in-person for 16 weeks (baseline, 4 weeks, 8 weeks, and 16 weeks) with outcomes measured at each time point. These outcomes include: VIPA use and acceptability (Acceptability, Feasibility, and Appropriateness Scale); Social Isolation (PROMIS-Short Form 8a); Anxiety (GAD-7); Self Efficacy for Managing Social Interactions (PROMIS-Short Form 4a); Ability to Participate in Social Roles and Activities (PROMIS-Short Form 4a); Companionship (PROMIS-Short Form 4a); Geriatric Depression Scale (GDS – Short Form)functional status (PROMIS-Physical function); Cognitive Function (Brief MOCA); and Quality of Life/Well-being (Neuro-QOL Positive Affect & Well-Being). Demographics will be collected at baseline, and technology use data (adapted from Teacher Technology Integration Survey (TTIS)) will be collected at baseline and 16 weeks. We will also continue to collect feedback to iteratively optimize the technology, protocol, and implementation.

DATA AND SPECIMEN BANKING

Upon completion of all study activities, a final de-identified dataset will be created. This dataset will be stored indefinitely on the GIM server for secondary analyses. Only authorized personnel will have access to the dataset.

SHARING RESULTS WITH PARTICIPANTS

Study results will not be shared with participants or anyone else.

STUDY TIMELINES

Aim 1 will be conducted during months 1-7 and Aim 2 will be conducted during months 8-24.

INCLUSION AND EXCLUSION CRITERIA

No subjects will be excluded on the basis of race or ethnicity.

In Aim 1, stakeholders will be eligible if they are:

1. Adults aged 21 or older;
2. English-speaking; and
3. Currently provide at least 2 hours of weekly clinical support (e.g. emotional, social, physical, task-related) to an older adult (>65 yrs.) who may be socially isolated

Or

1. Adults aged 65 years or older;
2. Patients of the Northwestern Medicine Geriatrics Program;
3. English-speaking;
4. Able to verbally consent

In Aim 2, participants will be eligible if they are:

1. Adults aged 65 years or older;
2. Homebound patients;
3. Able to access the internet;
4. English-speaking; and

STU#: STU00212384

5. Able to verbally consent

VULNERABLE POPULATIONS – N/A**PARTICIPANT POPULATION(S)**

Accrual Number:	Category/Group: (Adults/Children Special/Vulnerable Populations)	Consented: Maximum Number to be Consented or Reviewed/Collected/Screened	Enrolled: Number to Complete the Study or Needed to Address the Research Question
Local	Stakeholders (Aim 1)	50	50
	Older Adults (Aim 2)	40	40
Study-wide	Stakeholders (Aim 1)	50	50
	Older Adults (Aim 2)	40	40
Total:		90	90

RECRUITMENT METHODSAim 1: Recruitment of Stakeholders

The PI will send out an email invitation to relevant listservs including healthcare providers and caregivers who care for older adult patients to recruit stakeholders. Older adults will be identified by clinicians.

After receiving the email invitation, interested individuals will click on the online REDCAP survey link to complete the online screener to determine their study eligibility, or they will be contacted via telephone to complete the screener to determine their study eligibility. Eligible participants will then be able to access the consent form online to provide consent, or they will provide verbal consent via telephone. Once a participant consents to be in the study, they will receive an email from the research study team within two weeks which includes a link to a brief online survey for them to complete once they complete their 2-4 week trial period of the VIPA. Those who cannot access the online survey will receive a phone call from the study team, and they will complete the survey over the phone. The survey will include some demographic questions and will include questions for them regarding their experience/use of the Google Home/Amazon Alexa device which will help inform the design of the companion VIPA booklet.

An online or verbal consent will be obtained prior to the telephone survey.

Aim 2: Recruitment of Patients

This study will be presented to providers in the Northwestern Medicine Geriatrics Program and other Chicago-based clinics, and they will be asked to pass along study information flyers to potential patient/caregiver subjects. In addition, clinic staff can provide the research study coordinator (RSC) with the names and phone numbers of potential participants via encrypted email. Potential participants may also be approached in-person at senior events or by posting

STU#: STU00212384

flyers at senior facilities. Potential subjects who are interested in learning more about the study will then contact the research staff by phone, or the research coordinator will contact potential participants. Potential participants will learn more about the study and, if interested, be screened for eligibility. To supplement the patient pool for recruitment, potential participants will also be identified through reports generated by the Enterprise Data Warehouse (EDW). This list of patient names, medical record numbers, phone numbers, address, and date of birth will be compiled in a report that can be securely accessed and reviewed by study staff. The PI or trained research study coordinators (RSCs) will review the charts of identified patients to confirm eligibility that cannot be ascertained via the EDW. Among the remaining eligible patients, research staff will send the patient's clinician an Epic message with a list of their patients to review and remove any patients that should not be contacted within 3 days. The study staff will then contact identified patients and if they are interested in participating or learning more about the study, the RC will obtain verbal permission to ask the patient a brief series of questions to verify eligibility. If patients are eligible, the PI or RSC will engage patients in the verbal informed consent process, or patients will be able to access the consent form online to provide consent when appropriate. The first phone survey, the baseline survey, will then be conducted over the phone or in-person by the PI or RSC with the patient, or online for those who are comfortable.

COMPENSATION FOR PARTICIPATION IN RESEARCH ACTIVITIES

Aim 1: For their participation as a stakeholder, each geriatrics expert panelist or patient will be provided a Google Home or Amazon Alexa (VIPA) which has a value of approximately \$40, or a \$20 gift card if they already have a device. Stakeholders will use this Google Home or Amazon Alexa device as part of their study engagement, and they will be able to keep the VIPA after study completion.

Aim 2: For their use of the Google Home or Amazon Alexa device and companion booklet as well as completion of study interviews, each older adult patient will be provided a Google Home or Amazon Alexa (VIPA) which has a value of approximately \$40. This VIPA will be used throughout the study and they will be able to keep the VIPA after study completion. Patients will also receive a \$20 gift card after completion of the study. Patients will receive the gift card compensation by mail.

WITHDRAWAL OF PARTICIPANTS

Participants can choose to withdraw from the study at any time. If a participant chooses to withdraw from the research, any data collected up until the point of withdrawal will still be utilized as it will not include identifying information.

RISKS TO PARTICIPANTS

The risks of harm from being in this study are minimal. The most significant risk is that both stakeholders and patients will be using a VIPA which may result in a loss of confidentiality if someone else were to access the information gathered by the Google Home or Amazon Alexa device. However, the research team will not have access to the any of the information that may be gathered/stored on the VIPAs. Patients in Aim 2 may additionally experience distress or psychological discomfort while completing the phone surveys, especially when answering questions related to social isolation.

POTENTIAL BENEFITS TO PARTICIPANTS

We cannot promise any benefits to stakeholders or patients taking part in this research. However, possible benefits for stakeholders (Aim 1) include that as a result of participating in this study,

STU#: STU00212384

they may gain a better understanding of how to incorporate the use of VIPAs with patients/older adults that may be socially isolated.

For patients (Aim 2), benefits may include learning helpful strategies using a VIPA to manage self-isolation and being able to access tools that might help them develop better socialization and communication habits while being homebound.

DATA MANAGEMENT AND CONFIDENTIALITY

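### Aim 2 promises the device's impact on outcomes, but a single-group change from baseline cannot separate that from pandemic-related change

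*Protocol*

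**What the plan says.** Under OBJECTIVES, Aim 2 has two parts: feasibility and implementation of the VIPA with its booklet, and "its impact on clinical and functional outcomes for older adults with social isolation".

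PROCEDURES INVOLVED describes one group: "we will recruit a total of 20-40 older adult homebound patients who are likely to be socially isolated". After consent and set-up, "participants will be asked to use the VIPA and accompanying second iteration of the instructional booklet". The compensation section confirms that every Aim 2 patient is given a device. Survey times are listed as "baseline, 4 weeks, 8 weeks, and 16 weeks) with outcomes measured at each time point". No usual-care group, delayed-start group or repeated pre-device baseline is described. STUDY TIMELINES adds that "Aim 2 will be conducted during months 8-24".

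BACKGROUND names an outside influence on the same outcomes. It says distancing may bring more isolation, and it states: "The impact of COVID-19 necessitated social distancing and consequent loneliness on the health of older adults is an acute public health concern". It adds that pandemic-related changes in the health system may harm older adults' physical and mental health through diet, exercise, social stimulation and access to functional supports.

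STUDY ENDPOINTS gives the Aim 2 endpoint as completion of the 16-week programme. The protocol describes no test or model for the clinical scales.

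**The concern.** Impact is a causal word. To answer it, the study needs some view of what would have happened to these participants over the same 16 weeks without the device. The design supplies none: everyone is treated, and each person is compared with their own single baseline.

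This matters more than usual here because the protocol itself names a cause, outside the study and able to change over time, that acts on the domains being surveyed: isolation, companionship, social participation, anxiety, depression, physical function and well-being. If outside conditions ease during follow-up, scores may improve without any help from the device. If they worsen, or if function declines, a useful device may look useless or harmful. The impact clause could be answered wrongly in either direction, and nothing in the data would show which.

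**Working it through.** **Is there a figure to reproduce?** No. The protocol gives no effect size, SD, significance level or sample-size calculation for Aim 2. The calculation below is an illustration, and its assumptions are stated.

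**What the design identifies.** Let δ be the true device effect at 16 weeks and d the average change from all other causes, both in SDs of the change score. The mean change from baseline estimates δ + d. With everyone treated and one baseline, only the sum is estimable. Its bias as an estimate of δ is d, whatever the sample size n.

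**Inputs.**
- n = 20 and n = 40: the two ends of the Aim 2 recruitment range (PROCEDURES INVOLVED).
- δ = 0: set to isolate the effect of drift.
- d = 0.1, 0.2, 0.3: assumed.
- Two-sided 5% paired t-test: assumed.
- With a within-person correlation of 0.5 (assumed), the SD of change is √(2 × (1 − 0.5)) = 1 SD of the score, so the two scales coincide.

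**Formula.** The test statistic follows a noncentral t distribution with n − 1 degrees of freedom and noncentrality d√n. The rejection probability is P(|T| > t₀.₉₇₅), where the critical value is 2.093 for n = 20 and 2.023 for n = 40.

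| Drift d | n = 20: d√n | n = 20: significant | n = 40: d√n | n = 40: significant |
|---|---|---|---|---|
| 0 | 0 | 5.0% | 0 | 5.0% |
| 0.1 | 0.447 | 7.1% | 0.632 | 9.5% |
| 0.2 | 0.894 | 13.6% | 1.265 | 23.5% |
| 0.3 | 1.342 | 24.7% | 1.897 | 45.7% |

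The figures are per outcome. Nearly all of the excess lies in the direction of the drift: at n = 40 and d = 0.2, 23.4 of the 23.5 percentage points do. Doubling n makes a false signal more likely, because the bias stays at d while the standard error shrinks.

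**Could survey dates rescue the impact clause?** Months 8 to 24 are 17 months, about 74 weeks. Less 16 weeks of follow-up, this leaves about 58 weeks of possible entry, so a calendar-time term could in principle be fitted. Assume four visits, correlation 0.5, a common linear calendar trend and even entry. The standard error of the 16-week effect at n = 40 is 1/√40 = 0.158 SD without the term and 0.196 SD with it. The 95% half-widths are 1.96 × 0.158 = 0.31 SD and 1.96 × 0.196 = 0.38 SD. If entry spans only 26 weeks, the half-width is 0.60 SD.

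That is the price in precision. The assumptions are harder to meet:
- Within one person, calendar time and time since set-up advance together. The separation therefore rests wholly on early and late enrollees being comparable, and they come from mixed recruitment sources.
- Baselines must be device-free. PROCEDURES INVOLVED does not clearly place set-up after the baseline survey, and eligibility does not exclude people who already own a device.
- The trend must be simple.
- The intervention must stay the same over calendar time, yet PROCEDURES INVOLVED plans to keep refining the technology, protocol and implementation during the study.

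**The case against.** The strongest defence is that this is a self-described pilot. A single arm is a normal choice for feasibility, the formal Aim 2 endpoint is programme completion, and analysis of the clinical scales commonly belongs in a statistical analysis plan, which is not shown. All of that is true. It protects the feasibility aim, but not the impact clause beside it. No analysis plan could fully supply a comparison that the design lacks.

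A reader might infer more than the protocol supports:
- **That drift would be reported as a device effect.** The protocol contains no before-after test, significance rule or attribution statement. It supports only that the two could not be told apart.
- **That distancing determines how isolated these people are.** BACKGROUND says only that it may increase isolation, and first describes isolation and loneliness as common in older adults without tying this to COVID-19. The changes in diet and exercise are tied to the health system and are also hedged.
- **That season is a confounder the protocol recognises.** Season is never mentioned, and spread entry would average out part of a seasonal effect, though not a steady trend.
- **That restrictions were changing during Aim 2.** Month 1 is undated, so the October 2021 version date does not fix when months 8 to 24 fall.

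It is also fair that participants are homebound for physical or cognitive reasons, so distancing rules may affect them less. That could reduce the drift, but visits and outside support can still change. Finally, the illustration would fit any single-arm study. What is specific to this one is that its own text names the rival explanation.

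**Conclusion.** The point holds in a limited form. The impact clause of Aim 2 asks a causal question that a single-group, single-baseline design cannot answer, and the protocol itself gives reason to expect outside change in the same outcomes. The bias equals the drift, can run in either direction, and does not shrink with more participants.

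This conclusion rests on the design alone. The percentages depend on the assumed drift, test and significance level, and they show scale rather than predict a result. The feasibility and implementation parts of Aim 2 are unaffected. The correction should be made because it changes what the study may conclude and costs almost nothing.

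**What to change.** 1. In Aim 2, replace the wording "its impact on clinical and functional outcomes for older adults with social isolation" with: *change from baseline in clinical and functional outcomes (descriptive) for older adults with social isolation*.
2. Report each change as an estimate with a confidence interval.
3. Add one sentence stating that change will not be attributed to the VIPA because there is no concurrent comparison.

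**Cost.** A protocol wording change and a less favourable claim. It needs no extra patients, visits or survey items.

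**Optional.** A calendar-time term based on survey dates may be added as an exploratory sensitivity analysis, with its assumptions stated. It should not be used to restore the word impact.

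**If impact must stay.** The design would need a concurrent comparison, for example delayed start. Drift shared by both arms would then cancel, but with 20 per arm the 95% half-width is 2.024 × √(2/20) = 0.64 SD of change. At this sample size that would allow unbiased estimation but not a confirmatory test, so rewording is the proportionate choice.

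### Aim 2 surveys may be given by phone, online or in person at any visit, Brief MoCA included, with no rule to hold or record the mode, so change from baseline can be mixed with a change of mode

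*Protocol*

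**What the plan says.** Protocol, Procedures Involved (Aim 2 paragraph): "These participants will be surveyed over the phone, online, or in-person for 16 weeks". The schedule follows at once: "baseline, 4 weeks, 8 weeks, and 16 weeks) with outcomes measured at each time point". The outcome list covers self-reported isolation, anxiety, depression, companionship, function and well-being, and also "Cognitive Function (Brief MOCA". No instrument is exempted from the three modes.

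Protocol, Recruitment Methods (Aim 2), on how the first assessment is taken: "will then be conducted over the phone or in-person by the PI or RSC with the patient, or online for those who are comfortable". All three modes are therefore open at baseline as well as at follow-up.

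Protocol, Objectives (Aim 2): the aim includes assessing the intervention and "its impact on clinical and functional outcomes for older adults with social isolation".

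Protocol, Study Endpoints: "For Aim 2, the study endpoint will be the completion of the 16 week pilot program".

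On design and size, Procedures Involved says "we will recruit a total of 20-40 older adult homebound patients who are likely to be socially isolated to use the VIPA". No comparison group is described.

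The protocol does not say that a participant stays in one mode, that the mode is written down, or how the Brief MoCA would be given to someone who answers online.

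**The concern.** In a one-group study, impact on an outcome has to be read from change within the same people. That reading needs the measurement to be the same at both ends. If some participants answer a member of staff at baseline and a web form at week 16, or the reverse, their change contains any difference between the two ways of answering. A concurrent control group under the same rules would tend to carry the same shift and cancel it; here there is none.

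Two features of this study make it worth settling in advance. First, several outcomes are self-reports of isolation, mood and anxiety, where answering a person may differ from answering alone. Second, the Brief MoCA is a cognitive test. If it is completed online without staff present, help from someone else in the home cannot be excluded, and the protocol's own definition of homebound includes people who need another person in order to go out. Both are general considerations about such instruments; the protocol gives no data on either.

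At stake is whether an observed change in these outcomes can be interpreted. If the mode is not captured at the visit, an analysis plan may have no means of recovering it later.

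**Working it through.** **Is the mode fixed anywhere?** Setting the two relevant sections side by side:

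| Question | Procedures Involved (Aim 2) | Recruitment Methods (Aim 2) |
|---|---|---|
| Modes open | phone, online, in person | phone or in person with staff; online if comfortable |
| Visits covered | baseline, weeks 4, 8, 16 | baseline |
| Same mode within a participant? | not stated | not stated |
| Mode recorded? | not stated | not stated |
| Brief MoCA treated separately? | no, same list | not mentioned |

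The risks section speaks only of phone surveys, but it does not restrict the mode. The text therefore permits a change of mode between visits.

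**How large could the effect be?** The protocol states no alpha, effect size, SD or mode effect, so there is no figure of its own to reproduce. What follows is an illustration on assumed inputs.

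*Bias.* Let p0 and p1 be the shares using a given mode at baseline and at follow-up, and m its effect on the score relative to the alternative. Then

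bias in mean change = (p1 − p0) × m.

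It is the net shift that counts. If 40% switch, all in one direction, and m = 0.3 SD of the change score, the bias is 0.40 × 0.3 = 0.12 SD. If the same 40% split evenly between the two directions, the net shift is 0.20 − 0.20 = 0 and so is the bias in the mean.

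*Effect on a test of no change.* Take a two-sided 5% one-sample t test on the change score with no true change and bias b in SD of the change score. The statistic is noncentral t with n − 1 degrees of freedom and noncentrality b√n, and the critical values are 2.023 (n=40) and 2.093 (n=20).

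| Assumed b | b√n, n=40 | Rejection rate, n=40 | b√n, n=20 | Rejection rate, n=20 |
|---|---|---|---|---|
| 0 | 0 | 5.0% | 0 | 5.0% |
| 0.05 | 0.316 | 6.1% | 0.224 | 5.5% |
| 0.12 | 0.759 | 11.5% | 0.537 | 8.0% |
| 0.20 | 1.265 | 23.5% | 0.894 | 13.6% |

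*Sensitivity to the assumptions.* Now state the mode effect in SD of the score itself, at 0.2 to 0.5 SD, with a net shift of 25 to 50 percentage points and a within-person correlation rho of 0.5 to 0.7. The bias runs from 0.25 × 0.2 = 0.05 to 0.50 × 0.5 = 0.25 SD. With SE = SD × √(2(1 − rho)/n) and a normal approximation, the rejection rate runs from about 6% to 30% at n=20 and 6% to 53% at n=40. The width of these ranges shows that the size depends on the inputs chosen, not on anything in the protocol.

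**With the mode held constant.** p1 − p0 = 0 for every mode, so a constant additive mode effect drops out of the change score and the nominal 5% is kept.

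**The case against.** The strongest reply is that the protocol lists the modes available to the cohort and nowhere says that anyone will change mode. Going online "or online for those who are comfortable" reads as a personal preference, which may well be stable, and other wording suggests that phone is the usual mode. Flexible contact also has an evident purpose for homebound older adults during a pandemic. All of this stands: a change of mode is permitted, not certain.

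A reader might go further and infer a systematic move from an interviewer-led baseline to self-completion just as the intervention begins. The documents do not support that. The phone baseline is staff-led, and nothing suggests that phone follow-up is self-completed, so only a move to online would be a change of that kind; a participant may also start online and stay there. No direction or timing of switching can be read from the text.

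It is also fair to say that the protocol writes down no hypothesis test and no change-from-baseline analysis, and that its Aim 2 endpoint is completion. The error rates above therefore belong to a hypothetical test. This limits the weight of the point but does not remove it, because Aim 2 still sets out to assess clinical and functional impact, and the single group leaves within-person change as the only way to do so.

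Lastly, an assessment manual could specify how each instrument is given. None is shown, and the protocol's own text opens all three modes for the whole list.

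**Conclusion.** The point holds in a limited form. As written, the protocol lets the mode of administration vary between visits within a participant for every Aim 2 outcome, the Brief MoCA included, without recording it, and no comparison group would offset a net shift. Change from baseline can therefore be mixed with a change of mode. This touches the clinical and functional impact part of Aim 2; the completion endpoint is unaffected.

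Its size cannot be determined from the document. On an assumed bias of 0.05 to 0.20 SD of the change score, a nominal 5% test would reject in about 6%-23% of studies at n=40 and 6%-14% at n=20. These figures rest wholly on the assumed bias and on a test that the protocol does not specify. They should not be read as the error rate of this study, nor as evidence that a shift will occur. In a feasibility pilot of 20-40 people the weight is moderate, but the correction is cheap and has to be made before the data are collected.

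**What to change.** Amend the Aim 2 paragraph of Procedures Involved along these lines: each participant completes all four surveys in the mode used at baseline where possible; a different mode is used only to avoid a missed visit; the mode used is recorded at each visit; and the Brief MoCA is given live by study staff, by phone or in person and in the same mode throughout, not by online self-completion. Align the baseline sentence in Recruitment Methods (Aim 2) with this.

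The exception protects retention. It does let some switching back in, but the switches would then be few and visible in the data. How the recorded mode is used in the analysis is a matter for the SAP.

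Cost: one amended paragraph, one REDCap field, slightly less freedom in scheduling, and a short call at each visit for participants who otherwise answer online.
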